### Step 5: combine the estimates for the 100 datasets into I PE, and use mianalyze in order to give 1 p-value for the treatment comparison corresponding to each delta value fitted.

Skeleton code for this part may be based on the following.

PROC MIANALYZE PARMS(CLASSVAR=CLASSVAL) = PES;
 CLASS trtp region1 numpes psaecol agegr3
 MODELEFFECTS trtp region1 numpes psaecol agegr3;
 ODS OUTPUT PARAMETERESTIMATES = pes2;
RUN;

CONFIDENTIAL Page 126 of 139

# Secondary Endpoint: Change from baseline in Post-bronchodilator FEV1 at Week 52 – MAIN ANALYSIS

The SAS-Code is the same as defined below in Step 5, except that the main analysis will have no BY-Statement.

Please make sure that records for missing post-randomization visits of participants included in the analysis are artificially created. In the added records the value of the response variable will be missing, but the full information on covariates must be included. This is to create a full correlation structure per participant among (expected) study visits. Refer to below example for visualization with visit 3 to 6 expected:

Dataset as per recorded data: Participants 2 and 3 with missing visits

Participant	Treatment	Covariate	Baseline	Visit	Change from baseline
1	Brensocatib 10mg QD	X	X	3	X
1	Brensocatib 10mg QD	X	X	4	X
1	Brensocatib 10mg QD	X	X	5	X
1	Brensocatib 10mg QD	X	X	6	X
2	Placebo	X	X	3	X
3	Brensocatib 25mg QD	X	X	3	X
3	Brensocatib 25mg QD	X	X	6	X

Dataset with added records for missing visits (italic) but full information on covariates:

Participant	Treatment	Covariate	Baseline	Visit	Change from baseline
1	Brensocatib 10mg QD	X	X	3	X
1	Brensocatib 10mg QD	X	X	4	X
1	Brensocatib 10mg QD	X	X	5	X
1	Brensocatib 10mg QD	X	X	6	X
2	Placebo	X	X	3	X
2	Placebo	X	X	4	•
2	Placebo	X	X	5	
2	Placebo	X	X	6	•
3	Brensocatib 25mg QD	X	X	3	X
3	Brensocatib 25mg QD	X	X	4	•
3	Brensocatib 25mg QD	X	X	5	
3	Brensocatib 25mg QD	X	X	6	X

CONFIDENTIAL Page 127 of 139

# Secondary Endpoint: Change from baseline in Post-bronchodilator FEV1 at Week 52 – Tipping Point (Sensitivity Analysis)

**NOTE:** Steps 2 to 6 will be repeated varying delta ( $\delta$ ) for brensocatib and placebo. As described in step 3, &i\_act10. and &i\_pbo10, &i\_act25. and &i\_pbo25.. will be macro variables set to the delta adjustments for brensocatib and placebo respectively, for the 10mg vs Placebo comparison and the 25mg vs Placebo comparison.

### **Step 1:** Create a dataset i\_input1 containing 1 row per participant and the following variables

```
usubjid
         participants identifier
trtn
         participants treatment (1=active 25mg, 2=active 10mg,
         3=placebo)
region 1 stratification factor: region (set of 3 dummy (0/1) variables
         to represent Europe, ROW and Japan, With North America as
         reference category)
         stratification factor: sputum sample for Pseudomonas aeruginosa
psaecol
        at Screening Visit (1=positive or 0=negative as the reference)
numpes Stratification factor: number of prior PEs in the previous 12
        months (1= <3, 0= \ge 3 as the reference)
agegr3 age group: 0=adult, 1=adolescent (with Adult as reference category)
Baseline Baseline post-bronchodilator FEV1
wk40 Week 40 post-brochodilator FEV_1
wk52
        Week 52 post-brochodilator FEV1
```

### Step 2: Impute the intermittent (non-monotone) missing data

NOTE: Binary (0/1) variables will be used for the factors of region, pseudon numpes agegr3 to represent all levels (ie. 3 region binary variables representing Europe, ROW and Japan, with North America as the reference)

```
PROC MI DATA=i_input1 SEED=123456 NIMPUTE=100 OUT=i_mono;
   MCMC IMPUTE=MONOTONE NBITER=200 CHAIN=MULTIPLE PRIOR=JEFFREYS;
   VAR Europe ROW Japan pseudon numpes agegr3 baseline wk16 wk28 wk40 wk52;
RUN;
```

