#### 8.3.3.1. Main Analyses

The Main Estimand of the change from baseline in post-bronchodilator FEV1 (L) at Week 52 is the On-Study Estimand in which all observed data will be included in the analysis (see Section 2). The ITT Analysis Set (see Section 5.2) will be used for this Estimand. The derivation of the endpoint is detailed in Section 6.7.3. Tabulations described below will not be limited to Week 52 but summarize all scheduled time points.

Pre- and post-bronchodilator FEV1 assessments at baseline and Weeks 16, 28, 40, 52 will be summarized by treatment group using descriptive statistics. The summary will include changes from baseline, too.

Change from baseline in post-bronchodilator FEV1 (L) will be analyzed using a linear repeated measures model including treatment group, visit, treatment-by-visit interaction, sputum sample being classified as positive or negative for *Pseudomonas aeruginosa* at Screening Visit, the number of prior PEs [<3 or  $\ge$ 3] in the previous 12 months, stratification region (North America, Europe, Japan, and the Rest of the World), and age group (adult, adolescent) as fixed effects, and baseline value as covariate. The variance-covariance structure will be compound symmetric with the robust sandwich variance estimator (option EMPIRICAL in the PROC-Statement). This analysis will be performed in SAS using MIXED procedure. The OM option will be used to adjust the coefficients for the LSMEANS to reflect the observed data.

If the age group covariate creates estimability issues, it may be removed. If the model still does not converge after removing the age group covariate, other handling including using the parametric covariance estimator instead of the robust sandwich covariance estimator may be applied. When using the parametric covariance estimator, the restricted maximum likelihood (REML) estimator will be applied, with the variance-covariance structure being applied with the following sequence: UN -> TOEPH -> ARH(1) -> CSH. If the model still does not converge, the maximum likelihood estimator will be applied instead of the REML estimator, with the same sequence of the possible variance-covariance structures. The adjustment will be added to the footnote of the corresponding outputs.

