#### 8.3.3.2. Sensitivity Analyses

A tipping point analysis will be used to investigate the impact of missing data and to examine the robustness of the main analysis. The tipping point will be identified when the respective comparison is no longer statistically significant at two-sided  $\alpha$ = 0.05.

To explore the impact of missing data on the mean treatment effect, different assumptions of the effect will be evaluated by adding an additional penalty (delta) prior to analyzing the imputed datasets and combining the results. For each brensocatib dose comparison relative to placebo, the tipping point penalties (delta adjustment) will be applied in a bi-directional manner. The deltas or delta adjustments are pre-selected multiples of the observed treatment effect. If the observed mean treatment effect from the main analysis is x, the deltas to be investigated will range from -3\*x to 0 for the active arm, in increments of 10 mL. The delta adjustments to be applied to the imputed data in placebo arm will range from 0 to 3\*x. The increment or range may be refined based on the analysis results and the location of the tipping point.

All recorded data up to and including the Week 52 assessment (see Section 2) will be included. Missing data will be imputed using multiple imputation first based on the MAR mechanism. The imputation model will contain the same covariates as in the main analysis model (see Section 8.3.3.1). 100 separate complete data sets for each comparison within the pre-selected delta range will be generated and analyzed. Markov Chain Monte Carlo (MCMC) method will be used to fill intermittent missing values, e.g., missing values between reported visits, under the assumption of MAR, resulting in an intermediate data with monotone missing patterns. MCMC will use a separate chain for each imputation (multiple chains), a non-informative prior for the means and covariances, and 200 burn-in iterations before the very first imputation in each chain. For monotone missing data the regression method will be applied using a separate regression for each of the non-monotone imputed datasets. Results will be combined across imputations using Rubin's method (Rubin 1987). The relevant delta decrement grid for each brensocatib dose vs. placebo comparison will be populated with the corresponding p-value.

Technical details for the implementation in SAS can be found in Appendix I.

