### Step 3: Impute the monotone missing data using an adjustment for the delta tipping point adjustment.

Note; as separate deltas will be used for each of the 10mg and 25mg treatments, the model will be run twice using the deltas respective to each Brensocatib treatment group (act10/pbo10 or act25/pbo25).

```
PROC MI DATA=i_mono SEED=123456 NIMPUTE=1 OUT=i_nomiss NOPRINT;
BY _IMPUTATION_;
CLASS trtn;
VAR trtn Europe ROW Japan pseudon numpes agegr3 baseline wk16 wk40 wk52;
MONOTONE REG(baseline=trtn Europe ROW Japan pseudon numpes/DETAILS);
MONOTONE REG(wk16=trtn Europe ROW Japan pseudon numpes baseline/DETAILS);
```

CONFIDENTIAL Page 128 of 139

```
MONOTONE REG(wk28=trtn Europe ROW Japan pseudon numpes baseline wk16/DETAILS);
MONOTONE REG(wk40=trtn Europe ROW Japan pseudon numpes baseline wk16 wk28/DETAILS);
MONOTONE REG(wk52=trtn Europe ROW Japan pseudon numpes baseline wk16 wk28 wk40/ DETAILS);

MNAR ADJUST(baseline / SHIFT=&i_act10. ADJUSTOBS=(trtn="1" "2"));
MNAR ADJUST(wk16 / SHIFT=&i_act10. ADJUSTOBS=(trtn="1" "2"));
MNAR ADJUST(wk28 / SHIFT=&i_act10. ADJUSTOBS=(trtn="1" "2"));
MNAR ADJUST(wk40 / SHIFT=&i_act10. ADJUSTOBS=(trtn="1" "2"));
MNAR ADJUST(wk52 / SHIFT=&i_act10. ADJUSTOBS=(trtn="1" "2"));
MNAR ADJUST(baseline / SHIFT=&i_pbo10. ADJUSTOBS=(trtn="3"));
MNAR ADJUST(wk16 / SHIFT=&i_pbo10. ADJUSTOBS=(trtn="3"));
MNAR ADJUST(wk28 / SHIFT=&i_pbo10. ADJUSTOBS=(trtn="3"));
MNAR ADJUST(wk40 / SHIFT=&i_pbo10. ADJUSTOBS=(trtn="3"));
MNAR ADJUST(wk52 / SHIFT=&i_pbo10. ADJUSTOBS=(trtn="3"));
```

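### The SAP's FEV1 tipping-point code does not fit the imputation model the SAP text requires; a minor code error, probably with little effect at Week 52

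*SAP*

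**What the plan says.** SAP Section 8.3.3.2 says of the FEV1 tipping-point analysis: "The imputation model will contain the same covariates as in the main analysis model". Section 8.3.3.1 defines that main model as a "linear repeated measures model including treatment group, visit, treatment-by-visit interaction", with *P. aeruginosa* status, prior exacerbations, region, "and age group (adult, adolescent) as fixed effects, and baseline value as covariate". Age group may be dropped if it causes estimability problems.

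Appendix I gives the code in steps.

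- **Step 2** is an MCMC run that fills only the gaps needed to make the missingness monotone. Its variable list is "VAR Europe ROW Japan pseudon numpes agegr3 baseline wk16 wk28 wk40 wk52", and it has no BY statement.
- **Step 3** imputes the remaining monotone gaps by regression and adds the delta. Its variable list is "VAR trtn Europe ROW Japan pseudon numpes agegr3 baseline wk16 wk40 wk52". A typical equation is "MONOTONE REG(wk16=trtn Europe ROW Japan pseudon numpes baseline/DETAILS".
- The Step 3 penalty statements cover baseline as well as Weeks 16 to 52. The active-arm baseline statement begins "MNAR ADJUST(baseline / SHIFT=&i_act10", and placebo has a matching one.
- **Step 4** derives the analysed response as the visit value minus baseline.

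Appendix I then applies the same analysis to the QoL-B Respiratory Symptoms score.

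**The concern.** The text and the code specify different analyses. With no treatment term, Step 2 draws intermittent values as if the three arms were one population. With no age-group term, the Step 3 equations impute adolescents from a relation dominated by adults. A penalty on baseline makes little sense, because baseline is measured before treatment and enters the response with the opposite sign.

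The tipping point is the only missing-data sensitivity analysis that Section 8.3.3 lists for FEV1, and it supports two hypotheses in the gatekeeping procedure (H7 and H8). Through QoL-B the same scheme supports H11 and H12. SAP Section 13 does not mention the discrepancy. A programmer must therefore either follow the code and breach the text, or follow the text and depart from the code.

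**Working it through.** The documents state no figure on this point, so there is none to reproduce. The check sets the text beside the code and then considers size.

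**1. Covariates required and covariates used**

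| Required (8.3.3.1) | Step 2 list | Step 3 equations |
|---|---|---|
| Treatment | absent | present |
| Region, *P. aeruginosa*, prior PEs | present | present |
| Age group | present | absent from all five |
| Baseline | present | present in the four post-baseline equations |

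Age group is in the Step 3 variable list but in none of its equations. The estimability clause does not explain this, since Step 2 and the Step 5 analysis model both keep age group. Week 28 is not in the Step 3 variable list, yet it has its own equation, predicts Weeks 40 and 52, and receives a shift. The step is internally inconsistent as printed.

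**2. What the pooling in Step 2 can reach**

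Week 52 is last in the monotone order, so a missing Week 52 value is never intermittent and Step 2 never fills it. The pooling can affect Week 52 only indirectly, through earlier filled values used in the Step 3 regressions.

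A large-sample simulation illustrates this. Every input is an assumption: 200,000 per arm in two arms, SD 0.75 L, correlation 0.95 between visits, true effect 40 mL, 12% dropout after Week 16, intermittent missingness 5%, 15% or 30%, missing baseline 0% or 2%, no delta.

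| Contrast | Step 2 as written | Treatment added |
|---|---|---|
| Weeks 16–40, 30% intermittent | 35.2 to 37.7 mL | 38.4 to 42.0 mL |
| Week 52, all six scenarios | 39.1 to 41.1 mL | 39.2 to 41.0 mL |

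Scenario by scenario, the Week 52 result as written ran from 1.2 mL below to 0.4 mL above the result with treatment added, with no consistent sign. One limit: all simulated dropouts had Week 16 observed, so their own earlier visits had no gap other than baseline.

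**3. Age group**

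Adolescents are about 40 of 1,620 + 40 = 1,660 participants, and 40/1,660 = 2.4%. The post-baseline equations also condition on the participant's own baseline and earlier values.

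**4. Whom the baseline shift reaches**

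A missing baseline with any later value observed is a non-monotone pattern. Step 2 fills it, without a shift. Baseline reaches Step 3 still missing only if Weeks 16, 28, 40 and 52 are all missing too.

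For such a participant, take delta = −30 mL. The documents do not say whether a shifted value carries forward into later regressions, so both cases are shown.

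- *No carry-forward.* With the baseline shift: (−30) − (−30) = 0 mL. Without it: −30 − 0 = −30 mL.
- *Carry-forward*, at an assumed correlation of 0.95 throughout. The coefficients on each earlier value are 0.95, 0.95/1.95, 0.95/2.90 and 0.95/3.85. With the baseline shift, the cumulative shifts are 1, 1.95, 2.437, 2.765 and 3.012 times delta, so the net is (3.012 − 1) × (−30) = −60.3 mL. Without it, they are 0, 1, 1.487, 1.815 and 2.062, so the net is −61.8 mL.

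If u is the share with no value at any visit and m52 the share missing Week 52, the fraction of the mean penalty lost is u/m52 without carry-forward, and close to nothing with it.

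**5. How large u can be for FEV1**

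Protocol inclusion criterion 5 requires a qualifying post-bronchodilator FEV1 at Screening. Exclusion criterion 12 removes anyone unable to perform acceptable spirometry then. SAP Section 6.7.3 takes the latest qualifying assessment before first dose as baseline, screening visits included. Hence u should be near zero.

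**The case against.** The case for leaving this alone is that Section 8.3.3.2 states the model correctly and Appendix I is only implementation detail. The absence of Week 28 from one list looks like a typing slip. The analysis runs only if the main result is significant (SAP Section 6.2), and it does not feed the adjusted p-values. That limits the consequence. It does not remove the error: this is the prespecified code, and nothing elsewhere corrects it.

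Three stronger readings are tempting, and the documents do not support them.

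- *A reader might infer that the penalty is diluted in proportion to the share with a missing baseline, or even reversed when follow-up is observed.* It is not. Step 2 fills those baselines unshifted, before any delta is applied.
- *A reader might infer that the FEV1 result will look more robust than it is.* This is not shown. The Week 52 contrast barely moved in the illustration. Where pooling did matter, at Weeks 16 to 40, it shrank a positive effect, which works against brensocatib.
- *A reader might assume that the code runs silently as printed.* The SAS code was not run, and the Week 28 inconsistency leaves that open.

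**Conclusion.** The code departs from the text in three respects that can be read directly: no treatment in Step 2, no age group in the Step 3 equations, and no Week 28 in the Step 3 list. The baseline shift is a fourth fault, of logic; the text does not forbid it, but nothing justifies it either.

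The severity is minor. For the Week 52 FEV1 contrast the effect is probably small, for the reasons in points 2 to 5 of the working. The documents give no missing-data rates, so no firm size can be stated, and the simulated figures only illustrate assumed inputs.

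For QoL-B the treatment omission and the baseline shift carry over; the age-group point does not, because QoL-B is completed by adults only. The score is collected every two weeks, so there are more chances for intermittent gaps. It is given only where a validated translation exists (protocol Section 7.5.2), so some adults may have no score at any visit. If they are kept in the imputation dataset, which the SAP does not say, the baseline shift would reach them.

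**What to change.** In SAP Appendix I, for both dose runs:

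1. Add two treatment indicators to the Step 2 variable list. This gives each visit its own treatment coefficient. It is preferable to running Step 2 separately by arm, because only about 8 adolescents are planned for placebo and an age-group term would be poorly estimated there.
2. Add `agegr3` to each of the five Step 3 equations, subject to the estimability clause in Section 8.3.3.1.
3. Add `wk28` to the Step 3 variable list, between `wk16` and `wk40`.
4. Delete the active and placebo baseline penalty statements.

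Carry items 1 and 4 into the QoL-B version. The cost is a few lines of code with no new data, best done before unblinding.

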### Step 3: Impute the monotone missing data using an adjustment for the delta tipping point adjustment.

Note; as separate deltas will be used for each of the 10mg and 25mg treatments, the model will be run twice using the deltas respective to each Brensocatib treatment group (act10/pbo10 or act25/pbo25).

```
PROC MI DATA=i_mono SEED=123456 NIMPUTE=1 OUT=i_nomiss NOPRINT;
BY _IMPUTATION_;
CLASS trtn;
VAR trtn Europe ROW Japan pseudon numpes agegr3 baseline wk16 wk40 wk52;
MONOTONE REG(baseline=trtn Europe ROW Japan pseudon numpes/DETAILS);
MONOTONE REG(wk16=trtn Europe ROW Japan pseudon numpes baseline/DETAILS);
```

CONFIDENTIAL Page 128 of 139

```
MONOTONE REG(wk28=trtn Europe ROW Japan pseudon numpes baseline wk16/DETAILS);
MONOTONE REG(wk40=trtn Europe ROW Japan pseudon numpes baseline wk16 wk28/DETAILS);
MONOTONE REG(wk52=trtn Europe ROW Japan pseudon numpes baseline wk16 wk28 wk40/ DETAILS);

MNAR ADJUST(baseline / SHIFT=&i_act10. ADJUSTOBS=(trtn="1" "2"));
MNAR ADJUST(wk16 / SHIFT=&i_act10. ADJUSTOBS=(trtn="1" "2"));
MNAR ADJUST(wk28 / SHIFT=&i_act10. ADJUSTOBS=(trtn="1" "2"));
MNAR ADJUST(wk40 / SHIFT=&i_act10. ADJUSTOBS=(trtn="1" "2"));
MNAR ADJUST(wk52 / SHIFT=&i_act10. ADJUSTOBS=(trtn="1" "2"));
MNAR ADJUST(baseline / SHIFT=&i_pbo10. ADJUSTOBS=(trtn="3"));
MNAR ADJUST(wk16 / SHIFT=&i_pbo10. ADJUSTOBS=(trtn="3"));
MNAR ADJUST(wk28 / SHIFT=&i_pbo10. ADJUSTOBS=(trtn="3"));
MNAR ADJUST(wk40 / SHIFT=&i_pbo10. ADJUSTOBS=(trtn="3"));
MNAR ADJUST(wk52 / SHIFT=&i_pbo10. ADJUSTOBS=(trtn="3"));
```

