#### 8.3.5.1. Main Analyses

The Main Estimand of the change from baseline in QoL-B Respiratory Symptoms Domain Score at Week 52 is the On-Study Estimand in which all observed data will be included in the analysis (see Section 2). The population attribute for this Estimand is adult participants with NCFBE who meet all inclusion criteria and none of the exclusion criteria. The ITT Analysis Set (see Section 5.2) will be used for this Estimand.

Calculated Respiratory Symptoms score (items 29 to 37) will be summarized at baseline and change from baseline at Week 52 by treatment group using descriptive statistics. Single item responses (each question) will be summarized by treatment group in a shift table. Completion rates will be presented by time point (see Section 6.7.5.10).

Change from baseline of calculated Respiratory Symptoms score (items 29 to 37) at Week 52 will be analyzed using a linear repeated measures model including treatment group, visit, treatment-by-visit interaction, sputum sample being classified as positive or negative for *Pseudomonas aeruginosa* at Screening Visit, the number of prior PEs [<3, ≥3] in the previous 12 months and stratification region (North America, Europe, Japan, and the Rest of the World) as fixed effects, and baseline value as covariate. Given that the QoL-B will be administered every two weeks for a total of 26 time points, estimation of a complex variance-covariance structure with many parameters will be untenable. Therefore, the variance-covariance structure will be compound symmetric with the robust sandwich variance

CONFIDENTIAL Page 62 of 139

estimator. Results will be presented in the same manner as the analysis of "Change from Baseline in Post-bronchodilator FEV1 (L) at Week 52" (see Section 8.3.3), including a figure displaying the adjusted means and corresponding 95% confidence intervals at Week 52 by treatment group. The OM option will be used to adjust the co-efficients for the LSMEANS to reflect the observed data. The between-treatment differences and corresponding 95% CIs will be presented; the associated p-value for the adjusted mean difference will be compared to the appropriate alpha level per the multiple test procedure.

If the model fails to achieve convergence, similar handling described in Section 8.3.1.1 Main analysis for Change from Baseline in Post-bronchodilator FEV1 (L) at Week 52 will be applied and the adjustment will be added to the footnote of the corresponding outputs.

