#### **Notes:**

- \_IMPUTATION\_ variable represents an ID variable 1 to 100 representing the 100 imputed datasets from the step above.
- The macro variable &i\_act10 and &i\_act25. will contain the delta shift for actual treatment (25mg or 10mg) and &i\_pbo10 and &i\_pbo25. will contain the delta shift for the placebo treatment. The range of delta will be -3\*X to +3\*X by 0.01 litre increments, where X=observed treatment effect difference in litres (active placebo) at Week 52 for the main model analysis. In order to obtain a range of delta symmetrical around 0, X will be rounded to 2 decimal places prior to multiplication. For example, if the treatment difference (25mg placebo) in FEV1 at Week 52 = 0.01 litres, the following table of deltas will be used in order to calculate the p-values corresponding to the grey shaded boxes. A delta of 0ml corresponds to no delta increment/decrement.

Table 20: Secondary Endpoint - Change from Baseline (FEV1): Tipping Point Analysis - Delta Increment / Decrement

				Brensocatib 25 mg – Placebo = $10 \text{ ml } (0.01 \text{ litres}) = x$					
						Active De	elta		
			-30 ml	-20 ml	-10 ml	0 ml	+10 ml	+20 ml	+30 ml
			-3*x	-2*x	-1*x	0	+1*x	+2*x	+3*x
	-30 ml	-3*x							
Delta	-20 ml	-2*x							
De	-10 ml	-1*x							
	0 ml	0*x							
Placebo	+10 ml	+1*x							
Pl	+20 ml	+2*x							
	+30 ml	+3*x							

CONFIDENTIAL Page 129 of 139

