### Secondary Endpoint: Change from baseline in QoL-B Respiratory Symptoms Domain Score at Week 52 – Tipping Point (Sensitivity Analysis)

The same analysis as described for Change from Baseline in Post-bronchodilator FEV1 (L) at Week 52 will be applied.

The range of delta will be determined in the same way using -3\*X to +3\*X by a suitable increment, where X=observed treatment effect difference (active – placebo) at Week 52 for the main model analysis. The increment will be selected in order to give suitable detail regarding the tipping point. In order to obtain a range of delta symmetrical around 0, X will be rounded to the same decimal places as the incremental parameter precision prior to multiplication.

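### The FEV1 tipping-point code shifts baseline and every visit inside a sequential imputation, so the delta that labels a result need not be the Week 52 penalty applied; QoL-B inherits the method

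*SAP*

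**What the plan says.** **Text.** SAP Section 8.3.3.2 has missing FEV1 values imputed first under MAR. It then explores departures by "adding an additional penalty (delta) prior to analyzing the imputed datasets and combining the results". Negative deltas go to the active arm and positive deltas to placebo, in 10 mL steps. In the Appendix I notes, Table 20 labels each cell by one active delta and one placebo delta in mL, and states: "A delta of 0ml corresponds to no delta increment/decrement".

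**Code.** Appendix I, FEV1 Tipping Point, works in steps.
- Step 2 fills intermittent gaps by MCMC, with no shift.
- Step 3 fills the remaining monotone gaps by sequential regression. The last regression is "MONOTONE REG(wk52=trtn Europe ROW Japan pseudon numpes baseline wk16 wk28 wk40/ DETAILS".
- The same Step 3 call carries one shift statement per time point, including "MNAR ADJUST(wk16 / SHIFT=&i_act10" and "MNAR ADJUST(baseline / SHIFT=&i_act10". Matching statements cover Weeks 28, 40 and 52, and the whole set is repeated for placebo.
- Step 4 defines the analysed variable as the visit value minus baseline.

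**QoL-B.** Section 8.3.5.2 and Appendix I carry the approach over: "The same analysis as described for Change from Baseline in Post-bronchodilator FEV1 (L) at Week 52 will be applied". No QoL-B imputation code is printed. Section 8.3.5.1, on the main model, says "QoL-B will be administered every two weeks for a total of 26 time points".

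**The concern.** A tipping point can be read only if the labelled delta is the penalty that was applied. Here the text describes MAR imputation followed by one addition, while the code puts a full delta on each visit within the imputation. A shifted Week 16 value used to predict Week 28, and so on, would give Week 52 its own delta plus a share of the earlier ones. That share depends on when the participant left, so one cell of Table 20 would mix different penalties. If dropout timing differed between arms, its two axes would not be on the same scale.

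The baseline statements raise a separate problem. Baseline is subtracted from the visit value, so moving it in the same direction as follow-up works against the penalty. Baseline also precedes treatment, so shifting it does not represent a departure from MAR after dropout.

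Both endpoints belong to the alpha-controlled families (Section 6.3.1, Families 4 and 6). The tipping-point results are the planned evidence that a significant finding survives missing data.

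By contrast, the primary endpoint's tipping-point code multiplies the post-withdrawal mean by its factor once, so label and penalty agree there.

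**Working it through.** **Table 20's own grid.** With x = 10 mL and multiples k = -3 to 3, k times x gives -30, -20, -10, 0, +10, +20, +30 mL. The printed grid reproduces.

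**Formula.** Let s_k be the shift carried by visit k, in units of delta. Observed visits have s = 0. If shifted values enter later regressions, s_k = 1 + sum over earlier visits j of b_kj x s_j, where b_kj are the regression slopes. If they do not, s_k = 1 at every imputed visit.

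**Assumed inputs.** The documents give no visit correlations, so two structures bracket the slopes.
- Exchangeable with correlation r: each of m earlier visits (baseline included) has slope r / (1 + (m - 1)r).
- AR(1) with correlation r: only the previous visit counts, with slope r.

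**FEV1 missing from Week 16, baseline observed, r = 0.9**
- Exchangeable slopes are 0.9/1.9 = 0.474, 0.9/2.8 = 0.321 and 0.9/3.7 = 0.243.
  - Week 16: 1
  - Week 28: 1 + 0.474 = 1.474
  - Week 40: 1 + 0.321 x 2.474 = 1.795
  - Week 52: 1 + 0.243 x 4.269 = 2.04
- AR(1), Week 52: 1 + 0.9 + 0.81 + 0.729 = 3.44

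**Week 52 penalty (x delta) by first missing visit, with feed-forward**

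| Assumed correlation | Wk 16 | Wk 28 | Wk 40 | Wk 52 | Mean |
|---|---|---|---|---|---|
| Exchangeable 0.80 | 1.99 | 1.54 | 1.24 | 1.00 | 1.44 |
| Exchangeable 0.90 | 2.04 | 1.56 | 1.24 | 1.00 | 1.46 |
| Exchangeable 0.95 | 2.06 | 1.57 | 1.25 | 1.00 | 1.47 |
| AR(1) 0.80 | 2.95 | 2.44 | 1.80 | 1.00 | 2.05 |
| AR(1) 0.90 | 3.44 | 2.71 | 1.90 | 1.00 | 2.26 |
| AR(1) 0.95 | 3.71 | 2.85 | 1.95 | 1.00 | 2.38 |

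The mean assumes dropout spread evenly over the four visits. Without feed-forward every entry is 1.00.

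**Simulation check.** The setting was three arms of 540, 20% monotone dropout (assumed), delta -30 mL on active and none on placebo. Added once, delta should move the Week 52 difference by 0.20 x (-30) = -6.0 mL, and the simulation gave -6.0 mL. With feed-forward it moved -8.8 mL (exchangeable 0.95) and -14.2 mL (AR(1) 0.95), which are average factors of 1.47 and 2.39.

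**Baseline.** Step 2 fills any missing baseline that is followed by an observed visit, without a shift. Step 3 therefore shifts baseline only when no later FEV1 value exists. The net shift in change from baseline is then s_52 - s_baseline.
- Without feed-forward: 1 - 1 = 0, so the penalty vanishes.
- With feed-forward: 1.79 x delta (exchangeable 0.80) to 3.52 x delta (AR(1) 0.95). Leaving baseline unshifted gives 1.99 and 3.71, so the offset is partial.

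**QoL-B, if all 26 visits are chained.** For the earliest dropout under AR(1) 0.9 the factor is (1 - 0.9^26)/(1 - 0.9) = 9.35.

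| Assumed correlation | Earliest dropout | Mean |
|---|---|---|
| Exchangeable 0.5 to 0.8 | 3.4 to 3.7 | 1.8 |
| AR(1) 0.7 to 0.9 | 3.3 to 9.4 | 3.0 to 6.8 |

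If only four visits were chained, the means would be 1.36 (exchangeable 0.5), 1.42 (exchangeable 0.7) and 1.86 (AR(1) 0.7).

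**The case against.** The strongest objection is that accumulation is not in the documents. It requires the software to pass the shifted value, not the unshifted draw, to the next regression, and the SAP does not say which happens. This stands: the supportable range starts at 1.0 x delta.

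A second objection is that the SAP calls delta a shift, so Table 20 labels the parameter correctly and one sentence defining it as a per-visit shift would be enough. That would cure the label. It would not make one delta mean the same penalty for early and late dropouts, bring the code into line with Section 8.3.3.2, or justify shifting baseline.

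Third, the main FEV1 model uses compound symmetry, under which the largest factor is about 2. However, that is a working structure with a sandwich variance, and the imputation regressions estimate their own slopes from the data.

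Fourth, the consequences are limited. Section 6.2 runs tipping points only when the main result is significant, no alpha-controlled p-value changes, and the grid may be refined. This stands.

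Several stronger readings are tempting, and the documents do not support them:
- **That the penalty is several times delta throughout.** For FEV1 the factor is 1.0 when only Week 52 is missing, and 2 or more on average only under AR(1).
- **That every imputed value is shifted.** Step 2 leaves intermittent gaps unshifted.
- **That the baseline lines turn the penalty into an advantage for brensocatib.** They offset or cancel it, and no computed case reversed it. Few FEV1 baselines should be missing, because the protocol requires acceptable spirometry at Screening and repeats it at Day 1.
- **That QoL-B is inflated about ninefold.** This needs a 26-visit chain, AR(1) 0.9 and dropout before Week 2. The 26 time points describe the main model, not the imputation.

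**Conclusion.** The point holds as a mismatch between SAP text and code. The code does not carry out the MAR-then-add sequence in Section 8.3.3.2, and its baseline adjustments have no valid role in a post-dropout penalty. How far the Week 52 penalty departs from the label is conditional on feed-forward, the assumed visit correlations and the assumed dropout pattern, none of which the documents give.

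A reader might infer that the error flatters the drug. For the participants who drive the analysis it does the reverse: an accumulated penalty makes the result tip at a smaller labelled delta, which understates robustness. Only the baseline shift works the other way, and for FEV1 it should touch few participants. QoL-B could have more missing baselines, because the questionnaire is given only where validated translations exist; its accumulation factor cannot be fixed until the visit set is specified. The main FEV1 and QoL-B tests are unaffected.

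**What to change.** In Appendix I, for FEV1 and QoL-B:

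1. Impute the monotone gaps under MAR in Step 3, with no shift. Keep a flag for the values imputed there, then add delta once to each flagged post-baseline value in a data step. Alternatively, apply the shift to Week 52 only. Either way the Week 52 penalty is 1.0 x delta for every dropout time, and the Table 20 label is the penalty applied.
2. Delete both baseline adjustment statements (active and placebo).
3. Name the visits that enter the QoL-B imputation.

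While the block is open, reconcile two smaller points. Week 28 is modelled and shifted in Step 3 but absent from its variable list. Age group is missing from the regressions, although Section 8.3.3.2 asks for the main-model covariates.

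The cost is a few lines of code and text, with no new data and no change to the main analyses.
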